5.4.2 Patients lost to follow-up

Several measures are taken to avoid patients from being lost to follow-up. The observational study documents handed over to investigators during the study set-up highlight the fundamental importance of patient follow-up and data collection throughout the study. The investigator will seek the means to contact the attending physician or the nearest trusted relation.

In the event of a missed visit, the investigation center shall contact the patient by phone several times (at least two documented calls) and send an appointment letter by certified mail. In the absence of a response, the attending physician will be contacted in a bid to obtain information on the patient's status and on all elements needed to trace a possible endoprosthesis related clinical event (hospitalization, surgery, etc.).

In the event that there are no results from the procedures below, then the alive/dead status of the patient must be documented in the eCRF once the investigator has confirmed it from the Epidemiological Center for the Medical Causes of Death (Cépi-DC).

Note: the patient may not be considered lost to follow-up by the investigator as long as the follow-up period (5 years) has not elapsed.

5.5 Deviations from the Clinical Investigation Plan

A deviation from the observational study (deviation from the protocol) occurs when the investigator or a member of the center involved in the observational study does not conduct the study according to the Clinical Investigation Plan, or according to existing regulations.

In this observational study where patients are treated per the standard practice of each center, a deviation report is only required in a limited number of cases. A deviation form must be completed for each deviation from the protocol, particularly in the following cases:

- If the patient does not receive proper information for the collection of his/her personal data
- Wrong version of the information note used
- Included patient does not meet all the eligibility criteria

5.6 *Scientific Committee*

A Scientific Committee common to all manufacturers has been established. This multidisciplinary and independent Committee is composed of one methodologist and several practitioners (vascular surgeons, interventional radiologists, etc.) the make-up of the committee being shown in APPENDIX B.

6 QUALITY CONTROL PROCEDURE

The research will be supervised according to the manager's standard operating procedures. The research shall be conducted at the investigation centers and patient care shall follow ethical and medical guidelines.

Transcribing data into the case report form

The observational study data will be recorded by the participating doctors in a notebook or an eCRF or electronic case report form. The information provided in the doctor's questionnaire should match the information in the patient's record.

Data management

Systematic coherence control procedures shall be set up and documented. Correction procedures shall be followed. For the observational study data, requests (queries) shall be issued and sent to different centers for resolution.

Quality Assurance Procedure

Quality control is carried out continuously during the various stages of error correction, according to the manager's standard operating procedures.

7 **LEGAL & ETHICAL CONSIDERATIONS**

7.1 *CNIL [French Data Protection Agency] Declaration*

This observational study shall be subject to the modified version of the Data Protection law of January 6, 1978. Before its actual commencement, the processing of data collected in the observational study shall be subject to referral to the French Advisory Committee on Information Processing in Material Research in the Field of Health (CCTIRS), and then the French Data Protection Agency (CNIL).

7.2 *Information and Non-opposition Form*

The investigator must inform the patient about the nature and objectives of the data collection and answer all questions. Patients must be informed of their rights, prior to their enrollment in the study, in order to be able to refuse, if they so wish, the collection and transmission of personal data.

According to existing law, an informational note must be given to the patient and an informed consent must be signed by the patient in order to collect and transmit his/her personal medical data.

7.3 *Final Research Report*

The final research report will be written by the sponsor. This report will be sent to each of the investigators.

8 **DATA PROCESSING AND STORAGE OF RESEARCH RELATED DOCUMENTS AND DATA**

Documents pertaining to research must be stored by all parties involved for a period of 15 years after the end of the research.

This indexed storage will comprise at least:

- Successive versions of the protocol (identified by the version No. and date)
- The letters of correspondence with the manager
- A completed and validated case report form for each subject enrolled
- All appendices specific to the observational study
- The final report of the observational study

The database from which the statistical analysis was drawn must also be stored by the head of analysis (hard or soft copy).

9 DATA ANALYSIS AND REPORTS

[figure not shown]
9.2 *Statistical criteria for discontinuing the research*

No discontinuation criterion.

9.3 *How to manage missing, unused or invalid data*

Missing data will be listed and presented in a tabulated form.

Patients will be considered as censored at the date of the last observation.

9.5 *Right of access to data and source documents*

Individuals with direct access to data in accordance with existing legislative and regulatory provisions, notably articles L.1121-3 and R.5121-13 of the Public Health Code (for example, investigators, individuals responsible for quality control, and any individuals appointed to collaborate in trials) shall take all necessary precautions to ensure the confidentiality of information relating to experimental drugs, trials, subjects involved in trials, particularly as regards their identity, and results obtained therefrom. Data collected by these people is then anonymized.

9.6 Rules relating to publication

W. L. Gore & Associates, Inc. is the proprietor of all data, analyses and results relating to the GORE® TAG® or Conformable GORE® TAG® Thoracic Endoprosthesis and these may not be used or transmitted to a third party without prior consent therefrom. However, the center is free to independently use and develop data resulting from the medical records of its own patients, as also data and information:

- That were known to the center prior to its disclosure by manufacturers
- That are or become legally accessible to the public
- That are released from the seal of confidentiality by written agreement of the manufacturer

10 EXPECTED RISKS AND BENEFITS

10.1 Risks

This study does not lead to any change in patient management. Therefore, there is no additional risk to the patients from their participation in the study.

Risks related to the implantation of a thoracic endoprosthesis, specifically the implantation of GORE® TAG® and Conformable GORE® TAG® Thoracic Endoprostheses have been described in the User's Manual delivered with each device.

10.2 Benefits

Patients in this observational study will receive the same treatment as they would have received if they had decided not to participate in this study. Therefore, there is no direct benefit related to their participation in the study.

## LIST OF ABBREVIATIONS AND DEFINITION OF TERMS

AE	Adverse Event
CI	Confidence Interval
CRF	Case Report Form
CT-scan	Computed Tomography scan
FUP	Follow-up
LPPR	Liste des Produits et Prestations Remboursables (List of Reimbursable Products and Services)
MRI	Magnetic resonance imaging
SAP	Statistical Analysis Plan

# STATISTICAL ANALYSIS PLAN

## 1. OVERVIEW

This statistical analysis plan (SAP) describes the planned statistical analyses of the data collected in the course of the observational study of the GORE® TAG® thoracic endoprosthesis in the treatment of diseases of the thoracic aorta.

This SAP provides additional details concerning the statistical analyses outlined in the protocol (version dated 21SEP2015). The purpose of the SAP is to ensure the credibility of the study findings by pre-specifying the statistical approaches to the analysis of study data.

### 1.1. Study Objective

The objective of this study is to evaluate the usefulness of the technique in terms of efficacy and safety of use of the GORE® TAG® and Conformable GORE® TAG® thoracic endoprosthesis at 5 years, on a cohort of patients representative of the population treated in real life conditions.

### 1.2. Study Design

This study is an observational, prospective, multicenter, non-randomized, single-arm and open-label which 160 patients will be enrolled from approximately 30 investigational French sites.

### 1.3. Study Plan

[REDACTED]

[REDACTED]

[REDACTED]

[REDACTED]

[REDACTED]

[REDACTED]

[REDACTED]

[REDACTED]

[REDACTED]

#### 1.3.2. Study duration

The duration of the study will be determined by the duration of recruiting 160 consecutive patients within 30 potential investigation centers.

- Enrollment period for the 160 patients: 24 months
- Follow-up period for each patient: 5 years
- Total duration of the study: 7 years (84 months)

#### 1.3.3. Study Device

The study devices are the GORE® TAG® and Conformable GORE® TAG® thoracic endoprosthesis including any newer models [REDACTED]

## STATISTICAL ANALYSIS PLAN

### 1.3.4. Study Assessments

The following flowchart applies to the study:

Data	CRF Pré-op.	CRF Treatment	CRF Post-op.	CRF Follow-up	CRF AE	CRF Re-intervention	CRF Study Exit
Consent	X						
Eligibility criteria	X						
Imaging tests	X		X	X			
Clinical history	X						
Assessment of disease(s) and diagnosis(es)	X						
Implantation		X					
Information on the device used		X					
Post-operative assessment			X				
Post-operative follow-up at D1-D30, 1, 2, 3, 4 and 5 years				X			
Onset of complications		X	X	X	X		
Repeat vascular intervention						X	
Surgical conversion						X	X
Lost to follow-up							X
Death					X		X

## 2. STATISTICAL METHODS

### 2.1. General Statistical Considerations

#### 2.1.1. Descriptive Statistics in Summary Tables

- Continuous variables will be summarized using standard quantitative statistics: number of non-missing observations, mean, standard deviation, median, quartiles and range (minimum and maximum observed values). The number of missing observations will also be specified.
- Categorical variables will be summarized using classical frequency statistics: number of non-missing observations and percentages by categories. Percentages will be calculated on the number of non-missing observations and will be displayed using one decimal, the corresponding bilateral 95% CI will be presented if appropriate. The number of missing observations will also be specified.

#### 2.1.2. Inferential Analysis

Differences between groups in survival analysis will be addressed by the log-rank test.

#### 2.1.3. Handling Missing Data

No replacement of missing data is planned.

If a patient interrupts the study before the end of study, he/she will be considered as missing from his/her last follow-up.

Patients will be considered as censored at the date of the last observation in survival analyses.

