### 2.4.3. Endpoints Analyses

#### 2.4.3.1. Primary Analysis

The primary endpoint is the all-cause mortality rate over the long term, which is 5 years.

The 5-year mortality is defined for all deaths occurring between the time of surgery when the endoprosthesis was inserted into the arterial access and the last follow-up visit at 5 years.

It will be presented as a categorical variable (with the corresponding 95% bilateral CI), overall and by visit, and described over time by a survival curve as per the Kaplan-Meier method together with the associated estimators.

The primary endpoint will also be analyzed depending on the life-threatening emergency and by main indication for implant (aneurysm, dissection, ulcer and trauma).

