## 2.5. Derived Criteria Calculation

- A patient will be considered as fulfilling the eligibility criteria if:
  - Inclusion criterion 1 is ticked YES
  - Inclusion criterion 2 is ticked YES or date of informed consent is filled
  - Inclusion criterion 3 is ticked YES
  - Exclusion criterion 1 is ticked NO
  - Exclusion criterion 2 is ticked NO
- Total study duration will be calculated as:  
Total study duration = study exit date - procedure date +1  
If the procedure date is not available, the baseline date will be used instead.
- Study follow-up duration will be calculated as:  
Study follow-up duration = last FUP date available - procedure date +1  
If the procedure date is not available, the baseline will be used instead.  
If the visit date is not available, the corresponding last imaging date will be used instead.
- Body Mass Index will be calculated as:  
 $BMI = \text{weight (kg)} / (\text{height (m)})^2$
- Derived criterion “life-threatening emergency” will be derived as follows:
  - if vital urgency specify is “Aortic rupture” then life-threatening emergency will be “Yes: Aortic rupture”
  - else if vital urgency specify is “Dissection complicated by malperfusion” then life-threatening emergency will be “Yes: Dissection complicated by malperfusion”
  - else if vital urgency specify is “Other” then life-threatening emergency will be “Yes: Other”
  - else if vital urgency is “No” then life-threatening emergency will be “No”
- Derived criterion “procedure duration” will be calculated as follows:  
Procedure duration = procedure end time – procedure start time
- Derived criterion “exclusion of the aneurysm without endoleak” will be defined as follows:  
No maximum diameter of the aneurysm sac increase > 5 mm (compared to 1st post-op exam) and no type I or type III endoleak

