## CONFIDENTIEL / CONFIDENTIAL

## STATISTICAL ANALYSIS PLAN

- Derived criterion "exclusion of the false lumen without endoleak" will be defined as follows:  
"Exclusion of the main entry of the dissection" will be YES if:
  - no false lumen perfusion type Ia, Ib, III is ticked
  - and "Incorrect Deployment" is not ticked or "false lumen perfusion through a tear proximal to the device in an untreated segment (not an endoleak)" is not ticked
  - and "Status of false lumen located opposite the treated part of the aorta" is "Complete thrombosis"
 If the perfusion status is unknown or if the false lumen thrombosis status is unknown then "exclusion of the false lumen without endoleak" will be missing.
- Derived criterion "exclusion of the penetrating aortic ulcer without endoleak" will be defined as follows:  
No maximum aortic diameter of the ulcer increase > 5 mm (compared to 1st post-op exam) and no type I or type III endoleak
- Derived criterion "exclusion of the rupture site without endoleak" will be defined as follows:  
No type I or type III endoleak
- Mortality from thoracic disease is defined as any death occurring as a result of complication of aortic disease (rupture, conversion, etc.) or following any surgery intended to treat the aortic disease. It will be derived as follows:
  - If the death occurs within 30 days after the initial procedure or any re-intervention or
  - If the death is related to the disease
 Then mortality from thoracic disease will be "YES"
- An adverse event (or any other parameter that is not reported in a follow-up CRF) will be considered as having occurred
  - "at 1 month" if it occurs between the procedure (included) and 30 days after the procedure
  - "at 1 year" if it occurs between the procedure (included) and 365 days after the procedure
  - "at 2 year" if it occurs between the procedure (included) and 731 days after the procedure
  - "at 3 year" if it occurs between the procedure (included) and 1096 days after the procedure
  - "at 4 year" if it occurs between the procedure (included) and 1461 days after the procedure
  - "at 5 year" if it occurs between the procedure (included) and 1826 days after the procedure

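### SAP 2.1.3 does not use the vital status that the protocol has traced, so the categorical 5-year mortality rate can come out too high

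*SAP*

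**What the plan says.** **Collection.** When calls, a certified letter and the attending physician yield nothing, protocol 5.4.2 has the investigator confirm with the national cause-of-death centre whether the patient is alive or dead, and record the answer in the eCRF. Both outcomes are collected.

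**Analysis.** The visible SAP does not mention this source.
- On early leavers, SAP 2.1.3 says: "If a patient interrupts the study before the end of study, he/she will be considered as missing from his/her last follow-up".
- On denominators, SAP 2.1.1 says: "Percentages will be calculated on the number of non-missing observations".
- On the primary endpoint, SAP 2.4.3.1 says: "It will be presented as a categorical variable (with the corresponding 95% bilateral CI), overall and by visit". It adds a Kaplan-Meier curve. Tables 46-48 use the Type 4 layout, which has a row for missing patients.
- On censoring, SAP 2.1.3 says: "Patients will be considered as censored at the date of the last observation in survival analyses". Protocol 9.3 has nearly the same sentence. Neither document visibly defines the last observation, and one rule serves every survival analysis.

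**Dates.** SAP 2.5 assigns items recorded outside the follow-up form by date: "An adverse event (or any other parameter that is not reported in a follow-up CRF) will be considered as having occurred" at 5 years "if it occurs between the procedure (included) and 1826 days after the procedure". The flowchart in SAP 1.3.4 puts death on the AE and Study Exit forms. SAP 2.4.3.1 sets a different end for counting deaths, between the time the device was "inserted into the arterial access and the last follow-up visit at 5 years". SAP 2.5 also separates the last follow-up date from the study exit date, but only for duration summaries: "Study follow-up duration = last FUP date available - procedure date +1".

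**The concern.** Tracing exists to protect the primary endpoint from loss to follow-up. If a traced patient becomes missing at the last visit, the tracing result is not used. The crude rate is then taken among patients still in follow-up plus those who died before leaving. A death under observation always counts. A patient who would have survived has the whole five years in which to leave the denominator. So the crude rate rises even when leaving has nothing to do with prognosis.

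It rises further if a traced death is brought back by its date while a traced survivor is not. Kaplan-Meier is safe in the first case but not in the second.

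One undefined last-observation date also cannot suit every endpoint. A registry check shows that a patient is alive. It does not show that the patient has had no complication.

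At stake is the reported 5-year rate, in a study set up because long-term data were judged inadequate for reimbursement renewal. The visible text also leaves the choice of handling open until after the deaths are known.

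**Working it through.** The visible text gives no expected mortality or loss rate, so there is no stated figure to reproduce.

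**Inputs.** N = 160 (SAP 1.2). Assumed: true 5-year mortality p = 35%; share lost while alive before 5 years L = 5, 16 or 25%; constant hazards; loss independent of death; unchanged hazard after loss unless stated.

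**Step 1: split the lost patients.** Death hazard λ = −ln(0.65)/5 = 0.0862 per year. Loss hazard μ solves μ/(λ+μ) × (1 − e^(−5(λ+μ))) = L. Lost and surviving: s = 0.65 × (1 − e^(−5μ)). Lost and then dying: d = L − s. Expected deaths are 0.35 × 160 = 56.

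| Per 160 patients | L = 5% | L = 16% | L = 25% |
|---|---|---|---|
| Lost, then die | 1.6 | 5.3 | 8.4 |
| Lost, then survive | 6.4 | 20.3 | 31.6 |

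**Step 2: SAP 2.1.3 applied evenly (all lost patients missing).** Rate = (56 − lost who die)/(160 − all lost).
- 5%: 54.4/152.0 = 35.8%
- 16%: 50.7/134.4 = 37.7%
- 25%: 47.6/120.0 = 39.7%

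Kaplan-Meier censored at loss gives 35.0% throughout.

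**Step 3: mixed handling (traced deaths count by date, traced survivors missing), full tracing.** Rate = 56/(160 − lost who survive).
- 5%: 56/153.6 = 36.5%
- 16%: 56/139.7 = 40.1%
- 25%: 56/128.4 = 43.6%

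For Kaplan-Meier the share at risk is n(t) = e^(−λt) − e^(−5λ)(1 − e^(−μt)). The estimate 1 − exp(−∫λe^(−λt)/n(t)dt) over 0 to 5 years is 35.8, 37.8 and 39.7%.

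**Step 4: sensitivity.**
- Other mortality levels at 16% loss, same formulas: a true 25% becomes 27.1% (even) or 29.0% (mixed); a true 45% becomes 48.3% or 50.9%.
- Hazard doubled after loss, 16% loss: the truth is 37.5%. Even handling gives a crude 37.7%, nearly right, and Kaplan-Meier 35.0%, which is 2.5 points low.
- Sampling error: the 95% CI half-width at 35% is 1.96 × √(0.35 × 0.65/160) = 7.4 points. At 16% loss the shifts are 2.7 (even) and 5.1 points (mixed). Only the mixed shift at 25% loss, 8.6 points, exceeds 7.4.

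**Step 5: one date for complications.** Simulation with a true 20% complication rate, 16% loss and deaths censored:
- Event-free time runs to a registry date, and nothing after loss is captured: about 18%.
- Event-free patients are censored at the last annual visit, but later reports still count: 22.3%.
- Events and event-free time stop at the same date: 20.0%.

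**The case against.** **Who has interrupted.** Protocol 5.4.1 and 5.4.2 say a patient may not be called lost before five years have elapsed. A non-attender whose status is still being entered may therefore not have interrupted the study. A documented registry status is also, in ordinary language, an observation, so the censoring sentence may already take it in. Both points stand, but they do not settle the matter. Protocol 5.2 lists loss to follow-up as premature termination on the exit form, and no definition of the last observation is visible.

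**The asymmetry.** A reader might infer that the SAP itself orders traced deaths to count and traced survivors to drop out. It does not. Taken alone, SAP 2.1.3 makes both groups missing. The asymmetry appears only if that sentence is applied to survivors and the dated windows of SAP 2.5 to deaths. The definition of the endpoint as all deaths and the forms that carry death make the mixture possible, but it remains an inference.

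**A wider span.** A reader might also divide visit-observed deaths by all per-protocol patients and report a low-end bias. That borrows the denominator of the adverse-event layout (Type 8). The mortality tables are Type 4, so the documents do not support it.

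**Complications.** These are not seen only at visits. Protocol 5.2 has event-onset forms, 5.3 asks for reporting once the investigator is informed, and 5.4.2 has the physician asked about hospitalization and surgery. So the 18% case is a worst case. Censoring at the last visit while later reports count would create the opposite error.

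**Unseen text.** Protocol 9.1 is not shown, SAP 1.3 is redacted, and the SAP contents list no section 2.2. A rule may exist there, although the visible missing-data sections contain none.

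**Conclusion.** The concern holds in a limited form. For patients treated as having interrupted, SAP 2.1.3 and 2.1.1 together make the categorical 5-year mortality rate too high when hazard is unchanged after loss, although the protocol collects the information that would prevent this. Under the assumed 35% mortality, the excess with even handling is 0.8, 2.7 or 4.7 points at 5, 16 or 25% loss, and Kaplan-Meier is not affected. With mixed handling the excess is 1.5, 5.1 or 8.6 points for the crude rate and 0.8, 2.8 or 4.7 for Kaplan-Meier. The mixed figures describe a possible reading, not an instruction in the SAP.

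Mortality, loss and tracing completeness are all assumptions, and the effect is small at 5% loss. No decision threshold is visible, so no pass/fail result turns on this; the reported rate does. The shift is bias, which the confidence interval does not show. It should be corrected, with medium confidence because of the unseen text.

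**What to change.** Add to SAP 2.1.3:

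1. **All-cause mortality.** Use vital status from any source (visit, call, physician, registry) in the same way for deaths and survivors: event at the death date, otherwise censor at the last date known alive, capped at day 1826. Reconcile that cap with the 5-year-visit bound in SAP 2.4.3.1.
2. **Categorical tables.** Count patients confirmed alive at 5 years by any source as non-missing. Report how many have unknown status and how many are known from the registry only, alive and dead. Read the rate beside the Kaplan-Meier 5-year estimate already planned, because it stays too high when tracing is incomplete. With half traced, 16% loss and unchanged hazard, it is (56 − 2.6)/(160 − 12.8) = 53.4/147.2 = 36.3% against 35.0%.
3. **Complications, re-interventions and device events.** Do not censor at a registry-only alive date. Censor at the last date on which that event's status was ascertained (visit, imaging or documented physician contact), and count only events up to that date.
4. **Sensitivity analysis for mortality.** Ignore both deaths and survival known only from the registry.

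The cost is SAP wording and possibly one eCRF field for the date vital status was confirmed. Visits and patient care do not change. One limit remains: if untraced patients die more often, Kaplan-Meier is still low (36.3% against 37.5% with half traced, 16% loss and doubled hazard).
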